3. OVERALL STUDY DESIGN

This is a multicentre, randomised, controlled, open-label, pragmatic, phase 2 basket study to assess the efficacy and safety of plitidepsin in different groups of immunocompromised patients with coronavirus disease 2019 (COVID-19) who require hospital care.

Approximately 150 patients are foreseen for the study, divided in 4 different groups of immunocompromised patients:

[figure not shown]
- **Group 1** –Patients receiving immune-suppression due to haematopoietic or organ transplantation.
- **Group 2** – Patients receiving B-cell depleting therapies.
- **Group 3** – Patients receiving other immune-suppressive therapies.
- **Group 4*** – Other situations with immune deficiencies.

*Not applicable in Spain

Whenever a patient can be allocated to more than 1 group, the priority will be group 1 > group 2 > group 3 > group 4*. In groups 1, 2, and 3, patients will be randomised to receive best standard

care (BSC) ± other antiviral (if clinically indicated) on control arm and BSC + plitidepsin on experimental arm. Group 4* will not be controlled, as shown in [Figure 9](#).

*Not applicable in Spain

*Not applicable in Spain

Figure 9 Algorithm for Patient Assignment in NEREIDA Basket Trial.

Stratification:

- Group 1: ISARIC mortality (<9/≥9) | Type of graft (allogeneic haematopoietic/lung or intestinal/other)
- Group 2: ISARIC mortality (<9/≥9) | Disease (haematological neoplasm/other)
- Group 3: ISARIC mortality (<9/≥9) | Disease (neoplasia/other)
- Group 4*: Not applicable

*Not applicable in Spain

Study periods:

The study will include a Screening period, a Treatment period and a Follow-up period.

The Screening period starts once the patient has provided written informed consent and ends when the patient is randomised in the study. Parameters assessed during this time will serve as the baseline values. The screening procedures should be preferably performed within 24 h prior to administration of study treatment, allowing a maximum of 48 h prior to administration of study treatment if required.

The Treatment period starts on Day 1 (date of randomisation) to 24 h after the last dose of the antiviral therapy; if no antiviral was given in the control arm, then the treatment period will finish on Day 4, for data management purposes. Antiviral treatment must always be started on the randomisation date.

The Follow-up period starts after the end-of-treatment and lasts until the end-of-study.

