5.2.2 Treatment Discontinuation

Treatment discontinuation occurs when an enrolled patient ceases to receive the study treatment regardless of the circumstances.

The primary reason for any treatment discontinuation will be recorded on the patient's electronic Case Report Form (e-CRF).

A subject may stop the study treatment but desirably should continue to the end of study. Should a patient decide to prematurely discontinue the study treatment (refuses treatment), all efforts will be made to complete and report the observations as thoroughly as possible. He/she should be asked if he/she can still be contacted for further information. The outcome of that discussion should be documented in the medical records. Whenever possible, patients who receive at least 1 dose of plitidepsin and withdraw from the study will be followed for at least 31 days (± 3 days) after administration of the last dose of plitidepsin to follow-up on possible open TEAEs at withdrawal or for potential late-onset treatment-related TEAEs.

Patients will receive the study treatment(s) while it is considered to be in their best interest. Specifically, individual treatment of a given patient will be prematurely ended if:

- Unacceptable toxicity despite allowed/applicable medical prophylaxis or therapy.
- Intercurrent illness of sufficient magnitude to preclude safe continuation of the study treatment.
- Patient's refusal (follow-up has to be continued for those patients who refuse treatment, but do not withdraw consent) and/or non-compliance with study requirements.
- A major protocol deviation that may affect the risk/benefit ratio for the participating patient.
- Investigator's decision.

A rapid disease progression per se is not an indication for treatment discontinuation and needs additional clinical input. Patients who are withdrawn for any reason must not be re-treated in the context of this study at any time.

All cases of treatment discontinuation must be documented (date and reason) in the eCRF. Patients will be informed that they have the right to withdraw from the study at any time, without prejudice to their medical care, and are not obliged to state their reasons.

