[¥]Antiviral treatment period in both arms will end 24 h after administration of the last dose of the antiviral therapy. If no antiviral was given in the control arm, then the treatment period will finish on Day 4.

[†]See [Section 7.2.1 Adverse Events of Special Interest \(AESIs\)](#).

For patients included in the study (all randomised patients) but never treated, only the applicable forms at baseline and off-study visit modules of the e-CRF should be completed but SAEs occurring during screening period need to be reported (using paper SAE forms).

All cases of treatment discontinuation must be documented (date and reason) in the electronic case report form (eCRF). A subject may stop the study treatment but desirably should continue follow-up to the end of study.

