7.2 SAFETY AND TOLERABILITY ASSESSMENTS

Safety will be assessed throughout the study through clinical and laboratory safety evaluations. These include medical history at screening, physical examinations, vital sign measurements, saturation of oxygen (SpO₂) by pulse oximetry (or arterial blood gas analyses [PaO₂]), and its respective FiO₂ ([Appendix 7 - Imputation of FiO₂ from oxygen flow values. High-flow oxygen](#)

therapy), triplicate 12-lead ECGs, laboratory tests (haematology, coagulation, and chemistry), clinical AE monitoring, and verification of concomitant treatments.

Patients will be evaluable for safety if they have received any partial or complete treatment administration.

All adverse events (AE) and adverse reactions (ARs), based on clinical signs and symptoms and laboratory measurements, will be measured daily until Day 60 (± 3 days), except treatment-related adverse events, treatment-emergent adverse events of special interest, and SAEs that will be measured daily until resolution or stabilisation to at least Grade 1, or to an acceptable level according to the investigator and the Sponsor of his/her designated representative.

Adverse events will be elicited from the patient (or, when appropriate, from a caregiver, surrogate, or the patient's legally authorised representative) by the study site staff using a non-leading question such as "How are you feeling today?" or "Have you had any health concerns since your last visit?"

The investigator and any designees are responsible for detecting, documenting, and reporting events that meet the definition of an AE or SAE and remain responsible for following up AEs that are serious, considered related to the study treatment or the study, or that caused the patient to discontinue the study treatment (see [Section 7.4.2](#)).

Clinical Signs and Symptoms: AEs, including worsening of baseline signs and symptoms of disease observed by the investigator (preferably by the same physician for a same patient) or reported by patients to study nurses will be recorded and graded according to NCI-CTCAE version 5.0, accessible via internet (http://ctep.cancer.gov/protocolDevelopment/electronic_applications/docs/CTCAE_v5_Quick_Reference_8.5x11.pdf). All events, including those considered not related to the study drugs, must be reported in the eCRF.

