8.2 ANALYSIS POPULATIONS

8.2.1 Full Analysis Set (FAS) Population

All randomised patients who have taken at least 1 dose of study treatment (plitidepsin or control) and have completed follow-up for survival until day 30 (± 2). Patients who die before the end of follow-up period will also be included in the FAS population. FAS population will be analysed according to their randomised treatment arm.

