8.2.3 As Treated Population

All patients who received any exposure to study treatment (plitidepsin or control). As Treated population will be analysed according to the treatment they actually received.

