8.6.2.2 As Treated Population

All patients who received any exposure to study treatment (plitidepsin or control). As Treated population will be analysed according to the treatment they actually received.

Day 1 therapy is defined as any exposure to study treatment (partial or complete).

<NOTE: Due to the premature study closure no PP specific outputs or sensitivity analyses will be generated in populations other than the FAS for baseline and efficacy analyses and safety population for safety analyses>.

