11.3 Treatment Administration

Treatment compliance defined as the extent to which patients take medications as requested in the protocol will be measured as duration in days of antiviral exposure ((Last exposure date-First exposure date)+1), total number of infusions/doses administered, the number of infusions/doses where total amount was administered, the number of infusions/doses where total amount was not administered and the number of infusions interrupted will be listed and summarized using descriptive statistics where applicable.

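### The analysis sets require a dose of, or exposure to, study treatment, but neither document says whether a control given best standard care alone has had either

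*Protocol*

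**What the plan says.** Protocol 8.2.1 and SAP 8.6.2.1 define the FAS as "All randomised patients who have taken at least 1 dose of study treatment (plitidepsin or control") who also have survival follow-up to Day 30 or have died. The population line of the primary estimand (Protocol 8.5, SAP 11.6.1) repeats the one-dose condition, as does the key secondary estimand in SAP 11.6.2.

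The As Treated set in Protocol 8.2.3 is "All patients who received any exposure to study treatment (plitidepsin or control"). SAP 8.6.2.2 adds only that "Day 1 therapy is defined as any exposure to study treatment (partial or complete"). Protocol 7.2 says: "Patients will be evaluable for safety if they have received any partial or complete treatment administration".

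Under Protocol 3, control is BSC with an antiviral only where clinically indicated, and controls may, not must, receive one. The same section provides that "if no antiviral was given in the control arm, then the treatment period will finish on Day 4", for data management purposes. SAP 11.3 measures treatment administration as "duration in days of antiviral exposure" plus counts of infusions or doses.

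**The concern.** In the plitidepsin arm, a patient who starts the assigned strategy has by definition had a dose. In the control arm, a patient can follow the assigned strategy exactly and have no antiviral dose to record. If dose means antiviral dose, entry to the FAS depends on a clinical decision made after randomisation, with the allocation known, in one arm only. The controls left in would be those whose physicians chose an antiviral, and they need not resemble the plitidepsin arm.

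The same uncertainty reaches safety. SAP 11.7 dates treatment-emergent events from the start of the treatments, and that start has no stated meaning for a control on BSC alone. Two programmers working from these texts could produce different denominators for the primary endpoint and for the control safety column.

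**Working it through.** The plan gives no figure for this point, so there is nothing to reproduce. The check is a comparison of texts, followed by an illustration under stated assumptions.

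**Step 1. Which reading does the text support?**

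| Points to exclusion | Points to inclusion |
|---|---|
| The FAS and the estimand ask for a dose | Both set definitions name control as a study treatment |
| The treatment period is timed from the last antiviral dose | Control is itself BSC with or without an antiviral |
| SAP 11.3 counts antiviral days | As Treated asks for any exposure, not a dose |
| Protocol 7.2 asks for a treatment administration | Controls with no antiviral have a treatment period to Day 4 |

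No sentence in either document settles it.

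**Step 2. Effect if BSC-only controls are excluded.** Let q be their share, m0 their 30-day mortality and m1 the mortality of controls given an antiviral.

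- All controls: q × m0 + (1 − q) × m1.
- Retained controls: m1.
- Gap: q × (m0 − m1).

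With q = 50%, m0 = 30%, m1 = 10%: all controls 0.5 × 30% + 0.5 × 10% = 20%; retained 10%. With the risks reversed: all controls 20%; retained 30%. For q of 25%, 50% and 75% the gap is 5, 10 and 15 points. If m0 = m1 it is zero. For scale, the target reduction in Protocol 8.1 is 12.5 points (20% to 7.5%). All values of q, m0 and m1 are assumptions.

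**Step 3. Same question with overall control mortality held at the plan's 20%.** Retained mortality = (20% − q × m0) / (1 − q). With 20% mortality in the plitidepsin arm too, the true odds ratio is 1, and the apparent one is (0.20/0.80) divided by the retained control odds.

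| q | m0 | Retained control mortality | Apparent odds ratio |
|---|---|---|---|
| 10% | 10% | 21.1% | 0.93 |
| 10% | 30% | 18.9% | 1.07 |
| 25% | 10% | 23.3% | 0.82 |
| 25% | 30% | 16.7% | 1.25 |
| 50% | 10% | 30% | 0.58 |
| 50% | 30% | 10% | 2.25 |
| any | 20% | 20% | 1.00 |

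**Step 4. Does continued accrual help?** Protocol 5.4 recruits until the target number of FAS-evaluable patients is reached. To keep 20 evaluable controls per group, 20 / (1 − q), rounded up, must be randomised: 23, 27 or 40 at q = 10%, 25% or 50%. That restores the count but leaves the selection in place.

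**Step 5. The decision rule in the protocol.** This uses 20 patients per arm, independent Beta(1,1) priors, no borrowing, and true mortality of 20% in both arms. The chance of reaching the 65% posterior cut-off is about 0.36 without exclusion. At q = 25% it becomes 0.44 (m0 = 10%) or 0.27 (m0 = 30%); at q = 50%, 0.61 or 0.12. This is a simplification, not the planned hierarchical model, and the current SAP no longer produces the Bayesian outputs on which the rule depends.

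**The case against.** The strongest reply is that exclusion is nowhere stated. Control is named as a study treatment and BSC is part of control, so a patient on BSC alone is receiving what was assigned. It is hard to call a patient with a defined treatment period untreated. SAP 11.3 is a summary of administration, not a population definition. This stands: exclusion is one reading, not an established fact. It does not remove the problem, because the Day 4 rule is expressly for data management and no text links it to set membership.

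Three stronger readings are tempting, and the documents do not support them.

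- **Lost outcome data.** Protocol 5.7 says that for patients included ("all randomised patients) but never treated, only the applicable forms at baseline and off-study visit modules of the e-CRF should be completed". A reader might infer that deaths among BSC-only controls would go uncollected. But the note just above gives those controls a treatment period, Protocol 7.1.4 records death from Day 1 to Day 60, and Protocol 5.2.3 keeps patients on study until consent withdrawal, death or study termination.
- **Enrichment by inclusion criterion 4.** It requires that at least one antiviral has failed or cannot be used. Another may still be given, so the share of BSC-only controls cannot be inferred from it.
- **One-sided withdrawal follow-up.** Protocol 5.2.2 asks that, whenever possible, "patients who receive at least 1 dose of plitidepsin and withdraw from the study will be followed for at least 31 days". Its stated purpose is to follow open or late-onset adverse events after plitidepsin. It does not govern FAS membership and needs no change on this account.

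It is also fair to say that the magnitude is wholly assumed, and that after early closure SAP 6.0 plans no formal tests. Both stand.

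**Conclusion.** Membership of BSC-only controls in the FAS, the primary estimand population and the As Treated set is undefined. The literal reading would exclude them from one arm after randomisation; the other reading keeps them. A reader should not conclude that these controls have been dropped, or that the randomised comparison is already lost.

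The bias under the literal reading could run in either direction. It is zero if mortality is unrelated to antiviral use, and 10 points in the assumed case of half the controls and 30% against 10%. The documents give neither the share nor the risks.

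The point survives early closure. SAP Table 3 still reports mortality on the FAS and safety on the As Treated set, and SAP 6.0 still expects the arms to be compared numerically. The note in SAP 8.6.2.2 rules out analyses in other populations, so no all-randomised table would reveal an exclusion. With low recruitment, each patient moved in or out shifts a rate more. The Day 30 follow-up condition in the FAS definition is a separate matter, not judged here.

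**What to change.** 1. In Protocol 8.2.1 and 8.5 and SAP 8.6.2.1 and 11.6.1, report 30-day mortality in all randomised Group 1-3 patients, in the arm to which they were randomised, and remove the one-dose condition. Align SAP 11.6.2, which carries the same phrase.
2. In Protocol 8.2.3 and SAP 8.6.2.2, state that control exposure starts on Day 1 whether or not an antiviral is given. In SAP 11.7, count treatment-emergent events in controls from Day 1.
3. In Protocol 5.7, say that the rule for patients never treated does not apply to controls managed with BSC alone.

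The cost is a few sentences and, at most, a vital-status query for randomised patients not otherwise followed. Since recruitment has ended, the SAP wording does most of the work and should be settled before database lock. The downside is slight dilution, because plitidepsin patients who were never infused would count in their randomised arm.

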8.2.2 Per Protocol Population

A subgroup of the FAS population that includes all patients who do not have any important protocol deviations that would interfere with the collection or interpretation of the efficacy data. Important protocol deviations will be defined in the SAP. Per Protocol population will be analysed according to their randomised treatment arm.

8.2.3 As Treated Population

All patients who received any exposure to study treatment (plitidepsin or control). As Treated population will be analysed according to the treatment they actually received.

8.3 GENERAL CONSIDERATIONS

The design of the trial, the Bayesian analysis and the sample size is based on the 30-day (+/- 2 d) survival information on the FAS population. The analysis of the primary and other time-to-event efficacy endpoints will be performed primarily in the FAS but also in the “Per Protocol” and “As treated” populations. Supportive analyses will be performed on the Per Protocol population. Safety endpoints analyses will be based on the “As treated” population.

8.4 ANALYSIS METHODS

8.4.1 Primary Endpoint

The difference between treatment and placebo arms in all-cause mortality at 30 days will be examined using a Bayesian comparison of proportions within the calibrated Bayesian hierarchical model (CBHM) framework described by Chu and Yuan (93). The use of the CBHM allows for flexible information borrowing across all groups, with strong borrowing in the case when treatment effect is homogeneous among the groups and less borrowing as the effect becomes more heterogeneous.

In this framework the odds ratio is modelled as $\theta_i = \log(\text{odds}_i)$ with a normal distribution of unknown mean (μ) and variance (σ^2). The prior distribution used by the framework will be a minimally-informative prior using $N(0, 1)$.

The variance (σ^2) represents the degree of heterogeneity between the patient groups, with 0 representing the case where there is homogeneity of treatment effect and thus complete pooling of the results across patient groups, with adjustment for targeted p1 rates in each group, whereas a value closer to infinity would lead to no borrowing across groups. These estimates are iteratively updated within the modelling procedure based on the available data.

As each basket completes, they will be evaluated for efficacy, with information gained being used to update the analyses of successive baskets.

Once all patients recruited to a basket have completed the trial, a formal analysis will be performed on the patients within the basket. The result will be able to stand on its own for the

specific subpopulation, and the information from this analysis will be used to enrich the information at analysis of the proceeding baskets.

Results in later baskets will be related to pooled data, however if one basket is not seen to be homogeneous to other baskets, the information from that basket can be run without the pooled information from other baskets and its information not pulled through into later analyses.

As a sensitivity analysis the Bayesian hierarchical model will be used.

The cut-off for considering further clinical development of plitidepsin in each randomised group will be a posterior probability of superiority for the experimental arm equal to or greater than 65%.

Sensitivity/supportive analyses for the primary endpoint will be also performed. Frequentist approach for odds ratio comparison: unstratified and stratified considering randomisation and actual strata values.

